2.4.4.4 Multiplicity issues

Part 1: Dose escalation phase

Not Applicable.

Part 2: Treatment phase

In order to handle multiple secondary endpoints, the overall type-I error will be controlled by the use of a hierarchical approach. Statistical significance of the primary endpoint at the two-sided 0.05 alpha level is required before drawing inferential conclusions about first secondary endpoint (refer to order of list in [Section 2.1.3.2](#)). Inferential conclusions about successive secondary endpoints require statistical significance of the prior one.

This fixed hierarchical approach will ensure a strong control of the overall type-I error rate at the two-sided 0.05 level.

No further adjustments will be made for exploratory endpoints for which p-values will be provided for descriptive purpose only.

2.4.5 Analyses of safety data

Safety analyses will be performed on the safety populations (see [Section 2.3.2](#)), separately for Part 1 and Part 2 of the study. In Part 1, data will be presented separately for Japanese and non-Japanese patients.

In Part 2, safety data will be presented separately for the two following periods:

- Safety analysis of the 52-week blinded treatment period of Part 2. This analysis will present safety data collected up to the Week 52 visit (or end of treatment visit in case of premature treatment discontinuation before Week 52). Safety analyses will present safety data from the two treatment arms:
 - Placebo
 - GZ/SAR402671 15mg

- Safety analysis of the 104-week long-term follow-up period of Part 2. This analysis will present safety data collected from the Week 52 visit to the end of study, excluding the initial 52-week blinded treatment period. Only patients having received GZ/SAR402671 15mg during the long-term follow-up period will be included in this analysis. Safety analyses will present safety data from the following groups:
 - Delayed start: patients having received placebo during the 52-week treatment period, then having received GZ/SAR402671 during the long-term follow-up period.
 - Early start: patients having received GZ/SAR402671 during the 52-week treatment period, then having continued to receive GZ/SAR402671 during the long-term follow-up period.
 - All patients: all patients having received GZ/SAR402671 during the long-term follow-up period
- Safety analysis of the overall GZ/SAR402671 treatment period in Part 2. This analysis will present all safety data collected from the first intake of GZ/SAR402671 in Part 2 to the last intake of GZ/SAR402671 in Part 2 plus 6 weeks. All patients having received GZ/SAR402671 15mg in Part 2 (either during the 52-week blinded treatment period or during the long-term follow-up period) will be included in this analysis. Safety analyses will present safety data from the following group:
 - Overall GZ/SAR402671: patients having received GZ/SAR402671 during the 52-week treatment period and/or during the long-term follow-up period.

Details of timing of these two analyses is presented in [Section 4](#).

General common rules

The safety analysis will be conducted according to the Sanofi document BTD-009536 (version applicable at the time of database lock) “Analysis and reporting of safety data from Clinical Trials through the Clinical Study Report.”

All safety analyses will be performed using the following common rules:

- Safety data in patients who do not belong to the safety population (eg, exposed but not randomized) will be listed separately.
- The baseline value is defined in [Section 2.1.1](#)
- The potentially clinically significant abnormality (PCSA) values are defined as abnormal values considered medically important by the Sponsor according to predefined criteria/thresholds based on literature review and defined by the Sponsor for clinical laboratory tests, vital signs, and ECG (PCSA version dated 24 May 2014 [[Appendix A](#)])
- PCSA criteria will determine which patients had at least 1 PCSA during the TEAE period, taking into account all evaluations performed during the TEAE period, including unscheduled or repeated evaluations. The number of all such patients will be the numerator for the on-treatment PCSA percentage

- The treatment-emergent PCSA denominator by arm for a given parameter will be based on the number of patients assessed for that given parameter in the TEAE period by treatment arm on the safety population
- For quantitative safety parameters based on central laboratory/reading measurements, descriptive statistics will be used to summarize results and change from baseline values by time point and treatment arm. Summaries will include the endpoint baseline value, the last on-treatment value and change from baseline, the worst on-treatment value and change from baseline. The last on-treatment value is commonly defined as the last value collected during the treatment period (see [Section 2.1.4](#)). The worst on-treatment value is defined as the nadir and /or the peak post-baseline during the treatment period according to the direction (minimum or maximum) of the abnormality as defined in the PCSA list
- All measurements (scheduled or unscheduled) will be re-allocated as given in [Section 2.5.4](#), [Table 3](#) and [Table 6](#) and re-allocated visits measurements will be included in the by-time point summary
- The analysis of the safety variables will be essentially descriptive and no systematic testing is planned

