2.1.4 Safety endpoints

Observation period

The observation period will be divided into 4 periods:

- The pre-treatment period is defined as the time from the signed informed consent date up to the first double-blind IMP administration
- The on-treatment period is defined as the time from the first administration of the IMP to the last administration of the IMP + 1 day, including any temporary treatment discontinuation period, if any
- The residual treatment period is defined as the time from the last administration of the IMP + 2 days to the last IMP administration + 6 weeks
 - The treatment-emergent adverse event (TEAE) period will include both the on-treatment and the residual treatment periods
- The posttreatment period is defined as the period of time starting the day after the residual treatment period

Part 1: Dose escalation phase

Safety endpoints will be assessed by:

- Physical examination
- Neurological examination
- Clinical laboratory evaluations, including hematology, biochemistry, and urinalysis
- Vital signs
- Assessment of adverse events (AEs) and concomitant medication
- Ophthalmological examination. Visual acuity and lens evaluation will be performed according to the Lens Opacity Classification System II (LOCSII) for monitoring potential cataract development and worsening of pre-existing cataract.
- ECG

Part 2: Treatment phase

Safety endpoints will be assessed by:

- Physical examination.
- Neurological examination.
- Clinical laboratory evaluations, including hematology, biochemistry, and urinalysis.
- Vital signs.
- Assessment of adverse events (AEs) and concomitant medication.

- Ophthalmological examination. Visual acuity and lens evaluation will be performed according to the Lens Opacity Classification System II (LOCSII) for monitoring potential cataract development and worsening of pre-existing cataract.
- ECG

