2.4.5.1 Analyses of adverse events

Generalities

The primary focus of AE reporting will be on TEAE as defined in [Section 2.1.4](#). Pre-treatment and post-treatment adverse events (including SAEs and AESIs) will be described separately.

If an AE date/time of onset (occurrence, worsening, or becoming serious) is incomplete, an imputation algorithm will be used to classify the AE as pre-treatment, treatment-emergent, or post-treatment. The algorithm for imputing date/time of onset will be conservative and will classify an AE as treatment emergent unless there is definitive information to determine it is pre-treatment or post-treatment. Details on classification of AEs with missing or partial onset dates are provided in [Section 2.5.3](#).

Adverse event incidence tables will present by SOC, HLGT, HLT, and PT, for each treatment arm, the number (n) and percentage (%) of patients experiencing an AE sorting based on results of column all. Multiple occurrences of the same event in the same patient will be counted only once in the tables within a treatment period. The denominator for computation of percentages is the safety population within each treatment arm.

Sorting within tables ensures the same presentation for the set of all AEs within the observation period (pre-treatment, treatment-emergent, and post-treatment). For that purpose, the table of all TEAEs presented by SOC and PT sorted by the internationally agreed SOC order and decreasing frequency of PTs within SOC will define the presentation order for all other tables unless otherwise specified. Sorting will be based on results of column all.

Analysis of all TEAEs

The following TEAE summaries will be generated for the safety populations.

- Overview of TEAEs by treatment arm, summarizing number (%) of patients with any
 - TEAE
 - Serious TEAE
 - Treatment-emergent AESI
 - TEAE leading to death
 - TEAE leading to permanent treatment discontinuation
- All TEAEs by primary SOC, HLGT, HLT, and PT, showing number (%) of patients with at least 1 TEAE sorted by the SOC internationally agreed order. The other levels (HLGT, HLT, and PT) will be presented in alphabetical order. This table will be presented by treatment arm

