4 FINAL ANALYSIS

The final analysis will be conducted in two steps:

- First step: analysis of the 52-week blinded treatment period of Part 2 of the study:
 - The analysis of the 52-week double-blind treatment period of Part 2 of the study will be conducted when all patients from Part 2 have been randomized and have all their data up to Week 52 collected and validated, and will consist in the final analysis of the primary, secondary, and exploratory endpoints up to Week 52. The cut-off date for this first step analysis will be defined as the date the last patient from Part 2 completes the Week 52 visit of the double-blind treatment period. Efficacy data collected after the Week 52 visit will not be included in this analysis. The safety analysis will be performed on all safety data collected and validated at the cut-off date of the first step analysis, including safety data collected after the Week 52 visit, but before the cut-off date. This analysis will be conducted after a partial database lock and treatment unblinding.
- Second step: analysis up to Week 156 of Part 2 of the study:
 - The second analysis will be conducted at the end of the study and will consist of the final analysis up to Week 156. This analysis will be conducted after the final database lock.

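### The 52-week placebo-controlled safety analysis stops at the end-of-treatment visit for early stoppers, contradicting the SAP's own TEAE period of last dose plus 6 weeks

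*SAP*

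**What the plan says.** Four parts of the SAP bear on which data enter the Part 2 safety comparison.

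- **Section 2.1.4** defines the residual treatment period as running "from the last administration of the IMP + 2 days to the last IMP administration + 6 weeks", and adds: "The treatment-emergent adverse event (TEAE) period will include both the on-treatment and the residual treatment periods".
- **Sections 2.4.5 (common rules) and 2.4.5.1** build the tables on that period: "PCSA criteria will determine which patients had at least 1 PCSA during the TEAE period", and "The primary focus of AE reporting will be on TEAE as defined in" Section 2.1.4. Sections 2.4.5.3 to 2.4.5.8 also count laboratory, vital sign, ECG and examination abnormalities over the TEAE period.
- **Section 2.4.5 (Part 2 periods)** says that the two-arm analysis of the blinded period presents "safety data collected up to the Week 52 visit (or end of treatment visit in case of premature treatment discontinuation before Week 52"). It then lists two further analyses: one of the 104-week follow-up, restricted to patients dosed with GZ/SAR402671 in follow-up, and one of all GZ/SAR402671 time up to 6 weeks after last intake, with no placebo group.
- **Section 4** describes the "First step: analysis of the 52-week blinded treatment period of Part 2 of the study". It takes the safety data up to a cut-off at "the date the last patient from Part 2 completes the Week 52 visit of the double-blind treatment period", "including safety data collected after the Week 52 visit, but before the cut-off date".

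**The concern.** For a patient who stops treatment early, Section 2.1.4 counts the next 6 weeks as treatment-emergent, while Section 2.4.5 closes the two-arm analysis at the end-of-treatment visit. Two programmers could follow this SAP faithfully and produce different TEAE tables.

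Safety and tolerability against placebo over 52 weeks is a Part 2 secondary objective (Section 1.2.2.2), and this is the only placebo-controlled safety comparison in Part 2. Patients who stop early include those who stop because of adverse events, so what happens to them shortly after stopping is relevant to it.

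Section 4 adds a second uncertainty. It extends the data for the same analysis step beyond Week 52, when patients randomized to placebo have moved to GZ/SAR402671 15 mg (Section 2.4.4), and it does not say where those data are shown.

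**Working it through.** **Where a residual-period event goes.** Take an event that starts after the end-of-treatment visit of an early discontinuer but within 6 weeks of the last dose. By Section 2.1.4 it is a TEAE. If the limit in Section 2.4.5 is applied as written:

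| Analysis | Placebo patient | GZ/SAR402671 patient |
|---|---|---|
| 52-week two-arm analysis (2.4.5) | out: after the end-of-treatment visit | out: same reason |
| Long-term follow-up analysis (2.4.5, 2.3.2) | out: not dosed in follow-up | out: not dosed in follow-up |
| Overall GZ/SAR402671 analysis (2.4.5) | out: never took active drug | in, but with no placebo group |

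The post-treatment adverse event overview in 2.4.5.1 does not recover the event, because the post-treatment period starts the day after the residual period ends. By the same logic, a patient who completes Week 52 but does not enter follow-up loses the residual period after the Week 52 visit.

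**The Section 4 data span.** Section 2.4.5 ends the two-arm analysis at Week 52 and refers to Section 4 for timing. Section 4, for the same step, takes safety data to the cut-off, including data after Week 52. The TEAE definition in 2.1.4 does not settle the matter, because its on-treatment period runs from first to last IMP with no stop at the switch from placebo to active drug. The spans differ, and neither section links the later data in the first step to particular tables.

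**Size of the early-stop gap.** Inputs from Section 1.3.2 are 108 patients per arm (216 in total), a difference of 4.06, an SD of 10.01, two-sided alpha of 0.05, at least 80% power and about 10% early terminations or unevaluable patients.

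- The plan's own figure reproduces. A two-sample t-test with 97 evaluable per arm has 80.2% power, and 97 / 0.90 = 107.8, so 108 per arm. This confirms the 216 used below; the point does not otherwise depend on it.
- If the 10% were all early treatment stops: 216 × 0.10 = 21.6, about 22 patients.
- Each loses up to 42 days: 21.6 × 42 / 365.25 = 2.48, at most about 2.5 patient-years over both arms.
- For other assumed stop rates, per arm:

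| Early stops | Patients | Patient-years lost, at most |
|---|---|---|
| 5% | 108 × 0.05 = 5.4 | 5.4 × 42 / 365.25 = 0.6 |
| 10% | 10.8 | 1.2 |
| 20% | 21.6 | 2.5 |

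**The case against.** The strongest reply is that the table rules prevail. The common rules in 2.4.5 apply to all safety analyses, and 2.4.5.1 and 2.4.5.3 to 2.4.5.8 repeat the TEAE period table by table. The parenthesis about the end-of-treatment visit may only mark where the blinded period ends. That is a possible reading, but the SAP does not state it. If it is what the sponsor intends, the sentence in 2.4.5 is worded wrongly and still has to change.

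The amount is also small. At most 2.5 patient-years out of no more than about 216 in the blinded year is about 1% (2.48 / 216). The 10% is an efficacy sizing allowance, not a treatment-discontinuation rate. Section 2.4.4.1 equates 7 days with about 5 half-lives, so most of the 6 weeks falls after the drug has cleared. All of this stands. It limits the size but does not remove the contradiction, since the plan itself chose 6 weeks.

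A reader might go further in three ways that the SAP does not support.

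- **Active-drug events counted under placebo.** Section 4 gives the data cut for the first step. Section 2.4.5 closes the two-arm analysis at Week 52 and assigns later data to the delayed-start, early-start and overall GZ/SAR402671 groups. No sentence puts follow-up events in the placebo column, so this is an ambiguity and not a stated rule. A count of affected placebo patients would rest on a reading the text does not state, and the SAP gives no accrual time from which to size it.
- **Deaths dropping out.** Section 2.4.5.2 tabulates deaths by treatment received for the on-study, TEAE and post-study periods and lists them.
- **The weeks after stopping as the period of highest risk.** Nothing in the SAP says so, and adverse events that lead to stopping begin before the stop, so they stay in under either rule.

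**Conclusion.** The contradiction is in the text and the rule is wrong as written. Applied literally, Section 2.4.5 removes residual-period TEAEs of early discontinuers from the only randomized placebo comparison of safety, and no other Part 2 safety analysis restores a by-arm view of them; deaths are still tabulated. Section 4 leaves a separate ambiguity about where data after Week 52 are shown.

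The figure of about 22 patients and at most 2.5 patient-years is an illustration. It assumes that the whole 10% allowance is early treatment stops and that each patient loses the full 6 weeks. The SAP gives no discontinuation rate and no interval between last dose and end-of-treatment visit.

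The effect is on safety reporting that the SAP itself describes as essentially descriptive. The primary efficacy test, its alpha and its power are not touched.

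**What to change.** - **Section 2.4.5:** define the window for the placebo-versus-GZ/SAR402671 safety comparison, identically in both arms, as first double-blind dose to last double-blind dose plus 6 weeks, ended at the first follow-up dose of GZ/SAR402671 where there is one. Deleting the parenthesis alone is not enough, because the TEAE period in 2.1.4 has no stop at the switch to follow-up drug.
- **Section 4:** state that safety data after the first follow-up dose enter only the long-term follow-up and overall GZ/SAR402671 tables.

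The cost is SAP wording and one date derivation. Adverse events are already recorded until the end of the study (Section 2.1.4.1), so no new data are needed. The change should be made before the partial database lock and unblinding.

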2.1.4.1 Adverse events variables

Adverse event observation period

- Pretreatment adverse events are adverse events that developed or worsened or became serious from the signed informed consent date up to first administration of IMP
- TEAEs are adverse events that developed or worsened or became serious during the TEAE period (as defined in [Section 2.1.4](#))
- Posttreatment adverse events are adverse events that developed or worsened or became serious during the posttreatment period

All adverse events (including serious adverse events and adverse events with prespecified monitoring) will be coded to a lower-level term (LLT), preferred term (PT), high-level term (HLT), high-level group term (HLGT), and associated primary system organ class (SOC) using the version of Medical Dictionary for Regulatory Activities (MedDRA) currently in effect at Sanofi at the time of database lock.

Adverse events (including serious adverse events and adverse events of special interest) will be recorded from the time of signed informed consent until the end of the study.

Adverse events of special interest (AESIs) include the following terms (their complete descriptions are provided in the protocol):

- New or worsening lens opacities and cataracts
- Pregnancy occurring in a female patient entered in the clinical trial or in a female partner of a male patient entered in the clinical trial will be recorded as an AESI with immediate notification in all cases
- Increase in aminotransferase (ALT)
- Symptomatic overdose (serious or non-serious) with IMP: An overdose (accidental or intentional) with the IMP is an event suspected by the Investigator or spontaneously notified by the patient (not based on systematic pills count) and defined as at least twice the intended dose within the intended therapeutic interval, adjusted according to the tested drug

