- All TEAEs by primary SOC and PT, showing the number (%) of patients with at least 1 TEAE, sorted by the internationally agreed SOC order and by decreasing incidence of PTs within each SOC. This sorting order will be applied to all other tables, unless otherwise specified. This table will be presented by treatment arm
- Number (%) of patients experiencing common TEAE(s) (PT incidence $\geq 5\%$ in any treatment group) presented by primary SOC and PT, sorted by the sorting order defined above
- All TEAEs related to IMP by primary SOC and PT, showing the number (%) of patients with at least 1 TEAE, sorted by the sorting order defined above. This table will be presented by treatment arm
- All TEAEs by maximal severity, presented by primary SOC and PT, showing the number (%) of patients with at least 1 TEAE by severity (ie, mild, moderate, or severe), sorted by the sorting order defined above. This table will be presented by treatment arm

Analysis of all treatment emergent serious adverse event(s)

- All treatment-emergent serious adverse events by primary SOC and PT, showing the number (%) of patients with at least 1 serious TEAE, sorted by the internationally agreed SOC order and by decreasing incidence of PTs within each SOC. This table will be presented by treatment arm
- Listings will be provided for all serious adverse events (SAE)s by treatment arm during on-treatment period

Analysis of all treatment-emergent adverse event(s) leading to treatment discontinuation

- All TEAEs leading to treatment discontinuation, by primary SOC and PT, showing the number (%) of patients with at least 1 TEAE, sorted by the internationally agreed SOC order and by decreasing incidence of PTs within each SOC. This table will be presented by treatment arm

Analysis of all treatment emergent AESI

- All treatment-emergent AESI by primary SOC and PT, showing the number (%) of patients with at least 1 treatment-emergent AESI, sorted by the internationally agreed SOC order and by decreasing incidence of PTs within each SOC. This table will be presented by treatment arm.

Analysis of pretreatment and posttreatment adverse events

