2.4.5.8 Analyses of ophthalmological examination variables

Number and percentages of patients with any abnormal ophthalmological examination on any eye at any time (whether present at screening or not) as well as number and percentages of patients with any new onset of abnormal ophthalmological examination on any eye during the TEAE period (see [Section 2.1.4](#)) as per investigator (site ophthalmologist) assessment will be summarized. A listing will be provided for patients with new onset of abnormal ophthalmological examination on any eye during the TEAE period.

Number and percentages of patients with any definite worsening of lens opacity on any eye as well as number and percentages of patients with any possible worsening of lens opacity on any eye during the TEAE period (see [Section 2.1.4](#)) as per central reader assessment will be summarized along with a description of lens opacity grading according to the ARLNS grading system (1). A listing will be provided for patients with worsening (definite or possible) of lens opacity on any eye during the TEAE period.

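### The pooled GZ/SAR402671 safety summary gives lens events only as n (%); a summary by time on drug would be a cheap improvement, since no planned table gives the 156-week risk

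*SAP*

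**What the plan says.** SAP Section 2.4.5 sets out three Part 2 safety analyses.

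- **52-week analysis:** placebo against GZ/SAR402671, up to the Week 52 visit or the end-of-treatment visit.
- **Long-term follow-up analysis:** delayed-start, early-start and all-patient columns, from Week 52 to the end of study, "excluding the initial 52-week blinded treatment period".
- **Overall analysis:** a single group, "All patients having received GZ/SAR402671 15mg in Part 2 (either during the 52-week blinded treatment period or during the long-term follow-up period"), with data taken "from the first intake of GZ/SAR402671 in Part 2 to the last intake of GZ/SAR402671 in Part 2 plus 6 weeks".

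Section 2.4.4 gives the planned time on drug: 52 + 104 = 156 weeks for early start and 104 weeks for delayed start. Nothing in Section 2.4.5 excludes patients who stop early.

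Section 2.4.5.1 fixes the statistic: "Multiple occurrences of the same event in the same patient will be counted only once in the tables within a treatment period", and "The denominator for computation of percentages is the safety population within each treatment arm". The AESI table is one "showing the number (%) of patients with at least 1 treatment-emergent AESI", and the serious TEAE table has the same form. Section 2.1.4.1 lists "New or worsening lens opacities and cataracts" among the AESIs. Section 2.4.5.8 adds central-reader results as "Number and percentages of patients with any definite worsening of lens opacity on any eye", the same for possible worsening, a description of lens grading, and a listing.

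Patient-years of exposure are summarised (Section 2.4.3.1), but no event count is divided by them. Kaplan-Meier is specified only for exploratory efficacy endpoints (Section 2.4.4.3). Section 2.4.5 also says that safety analyses follow a sponsor document, BTD-009536, which is not at hand.

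**The concern.** If lens opacity accumulates with exposure, the useful long-term figure is the risk after one, two or three years on drug. A head-count percentage over patients observed for very different times does not give that. Its value depends on how many patients stop, when they stop, and how the hazard changes over time, as well as on the drug. Two studies with the same lens hazard but different discontinuation would report different percentages.

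The period tables close only part of the gap. The 52-week drug column covers year 1 for early-start patients. The delayed-start follow-up column begins at first drug intake and covers those patients' whole time on drug. The early-start follow-up column leaves out the first year. It cannot be added to the 52-week column, because the denominators differ and a patient can be counted once in each period. So the risk over 156 weeks on drug appears nowhere. What is at stake is the reading of the long-term descriptive report.

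**Working it through.** **Inputs from the SAP.** There are 108 patients per arm (Section 1.3.2). That figure reproduces: a two-sample t-test with difference 4.06, SD 10.01, two-sided 0.05 and 80% power needs 97 per arm, and 97/0.9 = 107.8, rounded up to 108. Planned time on drug is T = 3 years (early start) or 2 years (delayed start). The tail after last intake is w = 6/52 year. The SAP gives no figure for the overall safety analysis itself.

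**Assumed.** The SAP gives no event rate and no yearly stopping rate. I take a constant 5% yearly risk, or a linearly rising hazard with the same 3-year risk. A fraction d stops per year, independently of events, with d = 0, 0.1 or 0.3. Section 1.3.2 allows about 10% early terminations or unevaluable patients.

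**Formulas.**
- Cumulative hazard H(t) = H3·(t/3)^s, with H3 = −3·ln(0.95) = 0.1539; s = 1 constant, s = 2 rising.
- True risk R(t) = 1 − exp(−H(t)).
- Stopping hazard k = −ln(1 − d).
- Expected percentage in a column with planned time T: P(T) = ∫₀ᵀ k·e^(−ku)·[1 − e^(−H(u+w))] du + e^(−kT)·[1 − e^(−H(T+w))].
- Pooled percentage = [108·P(3) + nD·P(2)] / (108 + nD), with nD = 108·e^(−k) delayed-start patients reaching drug.

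**Pooled percentage against true risk.**

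| Hazard | True risk at 52 / 104 / 156 weeks | Pooled n (%) at 0 / 10 / 30% stopping per year |
|---|---|---|
| Constant | 5.0 / 9.75 / 14.3% | 12.5 / 11.2 / 8.7% |
| Rising | 1.7 / 6.6 / 14.3% | 11.3 / 9.6 / 6.6% |

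Examples with a constant hazard:
- No stopping: P(3) = 14.77% and P(2) = 10.28%; their mean is 12.53%.
- 10% stopping: P(3) = 12.80%, P(2) = 9.35%, nD = 97.2; (108 × 12.80 + 97.2 × 9.35)/205.2 = 11.2%.

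At a 2% yearly risk the pooled figure runs from 5.1% (no stopping) to 3.5% (30%), against a 156-week risk of 5.9%. At 10% yearly it runs from 24.0% to 16.7%, against 27.1%.

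**What the other columns show.** For the 52-week drug column I set T = 1 with no tail. At a constant hazard λ = 0.0513 and k = 0.1054, this is λ/(λ+k) × (1 − 0.95 × 0.90) = 0.327 × 0.145 = 4.75%, against 5.0%. The delayed-start column is P(2) = 9.35%, against 9.75%. With the rising hazard the two columns read 1.6% against 1.7% and 6.4% against 6.6%. At 30% stopping and a constant hazard, the delayed-start column falls to 7.6% against 9.75%.

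**Rates.** With a constant hazard, events over the planned exposure patient-years give 5.0 to 5.2 per 100 at 0 to 30% stopping, against a true 5.1. With the rising hazard, the rate per 100 patient-years at risk moves from 4.5 to 4.3 to 3.8 at 0, 10 and 30% stopping.

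**Precision** (constant hazard, 10% stopping). About 178, 152 and 68 patients are at risk at 52, 104 and 156 weeks. The last is 108 × 0.9^(3 − 6/52) × 0.95³ = 68, early start only. The Greenwood standard errors are 1.6, 2.2 and 3.0 points. The shift in the pooled figure from no stopping to 10% is 12.53 − 11.16 = 1.4 points.

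**Landmark timing.** Table 6 (Section 2.5.4) targets Week 104 at D730 and Week 156 at D1095. These fall (730 − 1)/7 = 104.1 and (1095 − 1)/7 = 156.3 weeks after D1. For delayed start, D1095 is (1095 − 365)/7 = 104.3 weeks after D365. A curve read at exactly 104 or 156 weeks would miss events found at on-target visits. If lens examinations follow the Table 6 visits (an assumption), the 156-week reading would be the Week 130 risk: 12.0% (constant) or 10.1% (rising), against 14.3%.

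**The case against.** The strongest reply is that nothing here is stated wrongly. The SAP never presents the pooled percentage as a risk at a given week, Section 2.4.5 calls the safety analysis essentially descriptive, and the overall group has no comparator. BTD-009536 may already require rates. The 52-week drug column and the delayed-start follow-up column come within about half a point of the 1- and 2-year risks at 10% stopping. Exposure is tabulated out to 156 weeks, and patients with lens worsening are listed. The event and stopping rates are assumed, and at 10% stopping the 1.4-point shift is smaller than the 3.0-point standard error at 156 weeks.

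Most of this stands, and it limits the point. It does not remove it: the columns do less well when stopping is heavier, and none of these outputs gives the 156-week risk. BTD-009536 cannot be checked, and this SAP specifies its safety tables in detail without one by time on drug.

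A reader might go further in three ways that the documents do not support.
- **That the pooled column is the only table running from first intake over the whole time on drug.** The delayed-start follow-up column does so too for its patients.
- **That a treatment comparison is biased.** The randomised 52-week analysis is separate, and no contrast of the overall group with placebo is planned.
- **That a standard Kaplan-Meier reading at exactly 104 and 156 weeks is enough.** The visit days above show why it is not.

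**Conclusion.** The point holds as a low-priority, cheap improvement. The pooled percentage for lens AESIs, central-reader lens worsening and serious TEAEs corresponds to no stated time on drug. In the base cases it ranges from 12.5% to 8.7% (constant hazard) or from 11.3% to 6.6% (rising hazard) through discontinuation alone. The main gap is risk beyond 104 weeks; the 1- and 2-year risks are roughly visible elsewhere when stopping is low.

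The sizes rest on assumed event rates, assumed stopping rates and stopping unrelated to lens risk. Confidence is medium, chiefly because BTD-009536 is unseen.

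**What to change.** Keep all n (%) tables. Add to Section 2.4.5, for the overall GZ/SAR402671 group:

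> Cumulative incidence (95% CI, number at risk) of lens opacity/cataract AESIs and of central-reader worsening of lens opacity, by time from first GZ/SAR402671 intake, will be given for the nominal 52-, 104- and 156-week examinations on drug. Each examination is assigned to its nominal time on drug with a visit window counted from first GZ/SAR402671 intake, so that an event found at the examination for a landmark counts at that landmark (or an interval-censored estimate is used). Patients without an event are censored at their last lens examination up to last intake + 6 weeks. As a secondary summary, patients with a first event per 100 patient-years at risk (exact Poisson 95% CI) will be given for lens events and serious TEAEs, overall and by early and delayed start.

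If BTD-009536 already requires this, a one-line cross-reference is enough.

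The cost is modest programming on data already collected. The 156-week estimate rests on early-start patients alone. The incidence estimate assumes that stopping is unrelated to lens risk, and the rate assumes a roughly constant hazard; the report should state both.
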